7.8 SAFETY ANALYSIS

All safety analyses will be performed on the TS, besides the analyses of MTD determination. These will be performed on the MTD evaluation set.

7.8.1 Adverse Events

The analyses of AEs will be descriptive in nature. All analyses will be based on the number of patients with AEs (not on the number of AEs). The analysis will be based on BI standards (6). AEs will be coded using the most recent version of MedDRA. According to the BI standards multiple overlapping or adjacent recordings (AE occurrences) of the same AE are collapsed into one AE event if all AE attributes are identical (lower level term, severity, action taken, therapy required, seriousness, reason for seriousness, relationship, outcome, AE of special interest (AESI) flag).

The analyses of AEs will be based on the concept of treatment-emergent AEs, where a treatment-emergent AE has an onset in the analysing treatment period. The AE analysis will be based on the on-treatment period which starts with the date of the first administration of study medication and ends 30 days after the last administration of study medication. AEs with an onset date in the screening period (time between informed consent date and date of the first administration of study medication) or follow-up period (time after the on-treatment period) will be tabulated and listed separately.

Sorting order: In AE tables, system organ classes (SOCs) will be sorted alphabetically and preferred terms (PTs, within SOCs) will be sorted by descending frequency.

Listings of AEs will be displayed by patient. The actual planned dose of BI 891065 will be derived and included in the listings. AEs will be reported with start day and end day as calculated from the first day of treatment with study medication. For listings displaying AEs during the screening or follow-up period, the start and stop day are calculated from the start of the respective analysis period.

The incidence of AEs overall, related AEs and serious AEs (SAEs) will be reported by severity according to common terminology criteria for adverse events (CTCAE) grades. Drug-related serious AEs will also be tabulated. Protocol-specified AESI will be analysed based on data reported in the eCRF.

AEs leading to death during the on-treatment period will be tabulated by SOC and PT. Reported fatal AEs during the follow-up period will be listed.

Other significant AEs are defined as serious and non-serious AEs that lead to dose reduction of BI 891065 or permanent discontinuation of study medication. Their incidence will be reported by severity according to CTCAE grades. A listing of patients who developed other significant AEs will be provided and a flag for serious and non-serious will be included. In addition, AEs leading to treatment interruption will be reported by severity according to CTCAE grades.

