5.2.6 Assessment of adverse events

5.2.6.1 Definitions of AEs

5.2.6.1.1 Adverse event

An AE is defined as any untoward medical occurrence in a patient or clinical investigation subject administered a medicinal product and which does not necessarily have to have a causal relationship with this treatment.

An AE can therefore be any unfavourable and unintended sign (including an abnormal laboratory finding), symptom, or disease temporally associated with the use of a medicinal product, whether or not considered related to the medicinal product.

The following should also be recorded as an AE in the CRF and BI SAE form (if applicable):

- Worsening of pre-existing conditions other than the underlying disease
- Changes in vital signs, ECG, physical examination and laboratory test results, if they are judged clinically relevant by the investigator

If such abnormalities already exist prior to trial inclusion, they will be considered as baseline conditions and should be collected in the eCRF only.

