5.2.6.2 Adverse event collection and reporting

5.2.6.2.1 AE Collection

The investigator shall maintain and keep detailed records of all AEs in the patient files.

The following must be collected and documented on the appropriate CRF(s) by the investigator:

- From signing the informed consent onwards until the 30-day follow-up-visit:
all AEs (non-serious and serious) and all AESIs.
- After the 30-day follow-up-visit until the individual patient's end of trial:
all related SAEs and all related AESIs.
- After the individual patient's end of the trial:
the investigator does not need to actively monitor the patient for new AEs but should report any new occurrence of cancer of new histology and trial treatment related SAEs and trial treatment related AESIs of which the investigator may become aware of by any means of communication, e.g. phone call. Those AEs should be reported on the BI SAE form (see section [5.2.6.2.2](#)), but not on the CRF.

The rules for Adverse Event Reporting exemptions still apply, please see section [5.2.6.2.4](#).

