7.3.5 Safety analyses

Adverse events will be coded using the Medical Dictionary for Drug Regulatory Activities (MedDRA). Standard BI summary tables and listings will be produced. All adverse events with an onset between start of treatment and end of the REP, a period of 30 days after the last dose of trial medication, will be assigned to the on-treatment period for evaluation.

All treated patients will be included in the safety analysis. In general, safety analyses will be descriptive in nature and will be based on BI standards. No hypothesis testing is planned.

Statistical analysis and reporting of adverse events will concentrate on treatment-emergent adverse events, i.e. all adverse events occurring between start of treatment and end of the REP. Adverse events that start before first drug intake and deteriorate under treatment will also be considered as 'treatment-emergent'.

Frequency, severity, and causal relationship of adverse events will be tabulated by system organ class and preferred term after coding according to the current version of the Medical Dictionary for Drug Regulatory Activities (MedDRA) at database lock.

Laboratory data will be analysed both quantitatively as well as qualitatively. The latter will be done via comparison of laboratory data to their reference ranges. Values outside the reference range as well as values defined as clinically relevant will be summarised. Treatment groups will be compared descriptively with regard to distribution parameters as well as with regard to frequency and percentage of patients with abnormal values or clinically relevant abnormal values.

Vital signs, physical examinations, or other safety-relevant data observed at screening, baseline, during the course of the trial and at the end-of-trial evaluation will be assessed with regard to possible changes compared to findings before start of treatment.

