4. CHANGES IN THE PLANNED ANALYSIS OF THE STUDY

All analyses described in the CTP will be carried out.

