6. GENERAL ANALYSIS DEFINITIONS

6.1 TREATMENT(S)

In Part A of this Phase I trial, treatments are not randomized. Different dose levels and dose schedule of BI 891065 monotherapy are being administered.

The data will be presented only for Part A, because Part B was cancelled, as mentioned earlier.

For safety summaries events that start from the first administration of any trial medication until 30 days (REP) after the last administration of any trial medication will be considered as having occurred “on-treatment”. If not specified otherwise, all safety tables will be based on the on-treatment period. Adverse events that have onset during the screening or the follow-up period will be displayed in separate listings from those that occurred during the on-treatment period. The MTD evaluation period will be defined as the period from 1st treatment administration (day 1) till day 21 inclusively.

Labels of each treatment period, the labels used for displays in the tables and listings in the CTR, as well codes, decodes, sort order and labels for each trial medication are provided in the TSAP technical documents.

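### The SAP defines treatment-emergent AEs by onset date alone, which contradicts the protocol's rule that AEs starting before first intake and worsening on treatment also count

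*SAP*

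**What the plan says.** **Protocol.** Section 7.3.5 assigns to the on-treatment period every AE with onset from start of treatment to the end of the residual effect period, 30 days after the last dose. It then extends the definition: "Adverse events that start before first drug intake and deteriorate under treatment will also be considered as" treatment-emergent. Section 5.2.6.2.1 has all AEs collected "From signing the informed consent onwards until the 30-day follow-up-visit", so the database will hold AEs that began before any drug was taken.

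**SAP.** Section 7.8.1 gives one criterion, a concept "where a treatment-emergent AE has an onset in the analysing treatment period". The on-treatment period "starts with the date of the first administration of study medication and ends 30 days after the last administration of study medication". By contrast, "AEs with an onset date in the screening period" go, with follow-up AEs, into their own tables and listings, and no exception is made for those that later worsen. Section 6.1 says the same: "Adverse events that have onset during the screening or the follow-up period will be displayed in separate listings", apart from the on-treatment ones, and safety tables use the on-treatment period by default. Section 4 reports no departure from the protocol: "All analyses described in the CTP will be carried out".

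**The concern.** The two documents give different answers to the question of which AEs enter the main safety tables. The protocol's extra clause covers a case that matters in a tolerability study: a symptom present before dosing that becomes more severe on drug. Under the SAP's wording, an event dated to screening stays with the screening events whatever happens to its grade later.

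Safety and tolerability of BI 891065 monotherapy is a stated objective of Part A, and Part A is all that remains to be analysed, since Part B was cancelled. Cohorts are small, so one patient more or less in a row of an AE table is visible. A reader of the report who relies on the protocol's definition would also not know that a narrower one had been used.

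**Working it through.** The point is one of definition. The documents give no figure to reproduce, so the check sets the texts side by side and then follows a single event through them.

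**1. What differs.** Both documents run the window from first dose to 30 days after last dose, so the windows agree.

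- Protocol 7.3.5: onset in the window, **or** onset before first dose with worsening on treatment.
- SAP 6.1 and 7.8.1: onset in the window.

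The difference is exactly the second group in the protocol's definition.

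**2. Can that group contain anyone?** Yes. AEs are recorded from consent. Protocol 6.2.1.1 places screening 1 to 14 days before first dose and lets it be extended with the sponsor's agreement. An AE can therefore start before dosing and still be running when dosing begins.

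**3. One event followed through.** Take an AE that starts in screening at a low grade and rises to a higher grade on treatment.

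- *Worsening entered as a new record.* The new record has an on-treatment onset date. SAP 7.8.1 merges overlapping or adjacent recordings only when every attribute, severity included, is the same, so the higher-grade record stays separate. It is counted under both definitions.
- *Grade updated on the existing record.* The onset date remains in screening. The event is treatment-emergent under the protocol and not under the SAP. It is left out of the on-treatment AE tables.

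**4. Which route do the documents prescribe?** Protocol 5.2.6.1.1 lists "Worsening of pre-existing conditions other than the underlying disease" among the things to be recorded as an AE, which supports the first route for conditions that existed beforehand. Neither document states the convention for an AE that itself began between consent and first dose. SAP 7.8.1 refers to a sponsor standard for AE handling (SAP reference 6), whose content is not reproduced.

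**5. Scale.** Inputs: about 12 patients in Part A (protocol 7.6) and a minimum enrolment of three per cohort (protocol 3.1). SAP 7.8.1 counts patients, not events.

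- One affected patient in Part A: 1/12 = 8.3 percentage points.
- One affected patient in a cohort of three: 1/3 = 33.3 percentage points.

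These are shifts for a given AE term. They arise only if the patient has no other on-treatment record that already places them in that row. They show what one patient weighs, not how many patients are affected.

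**The case against.** The strongest reply is that nothing need be lost. The protocol has worsening of pre-existing conditions recorded as an AE, and the SAP keeps recordings of different severity apart. If sites enter each grade increase as its own record, the onset rule captures it. That is right as far as it goes, and it is why the consequence is stated as conditional. It does not settle the matter, because the recording convention for AEs that began after consent is not written down.

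A second reply is that SAP Section 3 builds on protocol Section 7, and that Section 4 could be read as carrying protocol 7.3.5 forward. But the SAP is not silent here. It states its own explicit rule in two places, and a programmer following it would produce the narrower tables.

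Third, the exposure is narrow. Abnormalities present before inclusion are treated as baseline conditions, so their worsening is a new AE with on-treatment onset. Laboratory worsening also shows in the CTCAE shift tables of SAP 7.8.2. Screening-onset AEs do not vanish, since they have their own tables and by-patient listings. All of this stands and limits the size of the problem.

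Three stronger readings are tempting and are not supported:

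- *That the SAP necessarily drops these events.* A reader might infer this from the onset rule alone. Loss requires both a worsening and an update to the existing record.
- *That the DLT count or MTD is biased.* DLTs are identified by the criteria of protocol 4.1.7, reported as AESIs under 5.2.6.1.4, and displayed on their own under SAP 7.4.1. Nothing there passes first-cycle DLTs through the treatment-emergent definition.
- *That a percentage of patients affected can be stated.* It would need the share of patients with an AE between consent and first dose, the share of those AEs that worsen, and the share recorded by updating. The documents give none of the three.

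**Conclusion.** The inconsistency is real: the SAP's stated rule is narrower than the protocol's and is not declared as a change. It should be corrected. Its effect is possible but not demonstrated, and it is confined to AEs that start between consent and first dose, worsen on treatment, and are updated on the existing record. The documents do not allow the number of such events to be derived, and it may be zero. The conclusion rests on the wording of the two documents as given. If the sponsor's AE standard or the eCRF completion rules require a new record for every grade increase, the tables would not change, but the SAP text would still need to be aligned with the protocol.

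**What to change.** Add the worsening clause of protocol 7.3.5 to SAP 6.1 and 7.8.1. State that an AE with onset before first intake whose CTCAE grade increases after first intake counts as treatment-emergent, at the worsened grade, with its onset set to the date of worsening. Include such events in the on-treatment AE tables. If the narrower rule is intended, declare it in SAP Section 4 with a reason.

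The cost is one sentence in each section and one derivation rule. The rule works only if the date of worsening is available in the data. AE counts may rise slightly.

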7.8.2 Laboratory data

The analysis of laboratory data will be descriptive in nature and will be based on BI standards (7). The same on-treatment period as considered for the analysis of adverse events will be applied for laboratory values. Patients having at least one post-baseline laboratory value will be displayed in the descriptive analyses. Patients with missing CTCAE grade at baseline or no baseline value but with post-baseline values will be displayed in a new category “missing CTCAE grade at baseline” for those laboratory parameters where CTCAE grading is applicable. Descriptive statistics, including change from baseline and frequency of patients with transitions relative to the reference range, will be provided. CTCAE grades for applicable laboratory parameters will be calculated according to CTCAE v5.0.

For Primary laboratory tests listed in Table [7.8.2: 1](#), the following outputs will be presented:

- Descriptive statistics, including changes from baseline
- Shift tables in terms of:
 - CTCAE grade, for laboratory tests with CTCAE grade defined;
 - Upper and lower reference limits, for laboratory tests without CTCAE grades;
 - Multiples of upper reference limit for customized shift tables of ALP, ALT, AST, total bilirubin and creatinine.
- Frequency of patients with potential clinically significant abnormalities.

For secondary laboratory tests listed in Table [7.8.2: 2](#), analyses will be limited to frequency of patients with potential clinically significant abnormalities.

For other laboratory tests, only listing of observed values will be presented.

Analyse of descriptive statistics should use normalized lab values. Analyses of frequencies of patients with potential clinical significance, analyses of shift, and liver function categories tables should use converted values.

Table 7.8.2: 1 Primary laboratory tests

Table 7.8.2: 2 Secondary laboratory tests

| Label | Lab test name | Direction of interest | Potential Clinical significance rule |
|-------|----------------------------|-----------------------|---|
| ALB | Albumin | Low | A ¹ |
| APTT | Activated Prothrombin Time | High | A ^{1,2} |
| CA | Calcium | Low, High | A ¹ |
| CL | Chloride | Low, High | Low: <80 mmol/L and <baseline High: >120 mmol/L and >baseline No CTCAE defined |
| EOS | Eosinophils | High | >1.0*10 ⁹ /L and > baseline No CTCAE defined |
| GGT | Gamma Glutamyl transferase | High | CTCAE Grade 2 or higher |
| PHOS | Phosphate | Low, High | High: >1.7 mmol/L and >baseline Low: <0.7 mmol/L and <baseline No CTCAE defined |
| PROT | Serum Protein | High | >ULN and >baseline No CTCAE defined |
| PT | Prothrombin Time | High | >ULN and > baseline No CTCAE defined |
| URIC | Uric Acid | High | Females: >600 umol/L and >baseline Males: >650 umol/L and >baseline CTCAE based upon AE |

¹A= CTCAE grade 2 or greater with an increase of at least one CTCAE grade from baseline

²CTCAE grading will not consider symptoms presence of bleeding or use of anticoagulation.

Worst laboratory value and its CTCAE grade (highest CTCAE grade) over all courses will be calculated for each laboratory parameter.

The last laboratory value on treatment is the laboratory value of the last visit during the on-treatment period of each patient.

Laboratory values without CTCAE grading will be compared to their reference ranges and frequency tables will be provided for the number of patients within and outside the reference range at baseline, for the maximum value on treatment and for the last measurement on treatment.

Differential blood count:

Differential blood counts were to be measured in absolute values according to the CTP. In case a subject's differential blood count is reported in percentage, the following conversion will be applied:

$$\text{Differential } [10^9/\text{L}] = \text{Differential } [\%] * (\text{White blood cell count value} / 100)$$

The corresponding reference ranges of the converted differential blood values are not allowed to be converted like the individual laboratory measurements. The reference range is taken from the BI standard reference range definition.

Urine analysis based on dipstick:

To ensure medically rational and consistent BI internal handling of urine laboratory values assessed by dipstick only, no analyses based on CTCAE grades will be done for urine. For urine measurement based on dipsticks the indicated results will be converted as described in Table 7.8.2: 3 for the analysis and displayed in the urine analysis tables.

Table 7.8.2: 3 Conversion of urine measurements based on dipsticks

| Original dipstick measurement | Converted dipstick measurement |
|--|--------------------------------|
| “-” ; “NEG” ; “NEGATIVE” ; “NORMAL” | 0.0 |
| “0.5” ; “TRACES” ; “TRACE” ; “+/-” ; “+” ; “-/+” | 0.5 |
| “+” ; “1+”; “SMALL” | 1.0 |
| “++” ; “2+”; “MODERATE” | 2.0 |
| “+++” ; “3+”; “LARGE” | 3.0 |
| “++++” ; “4+” | 4.0 |

Handling of CTCAE grade -1 and -9 laboratory parameters:

Generally, in case only one direction of worsening (high or low laboratory value) is specified in the CTCAE document, there is no need to examine the other direction. Therefore, for calculating the change in CTCAE grade, patients with a CTCAE grade of -9 (no CTCAE grade defined) will be automatically treated as CTCAE grade 0 for all analyses. In laboratory listings, the CTCAE grade will be displayed as -9.

There are certain parameters for which CTCAE grades can only be attributed by taking physiological consequences into account. These laboratory values will be coded as -1. As these definitions aggregate laboratory data and adverse events or concomitant therapies no analyses based on CTCAE grades will be done. Instead standard laboratory analyses as for laboratory parameters without CTCAE grade definitions will be done. Nevertheless, a laboratory listing including -1 values will be added to the CTR.

Corrected calcium:

The grading of hypocalcemia is based on corrected calcium as calcium can be falsely low if hypoalbuminemia is present. The following corrective calculation will be performed:

$$\text{Corrected calcium (mg/dL)} = \text{Total Calcium (mg/dL)} - 0.8[\text{Albumin (g/dL)} - 4]$$

No correction of the reference range has to be done. The reported reference range of total calcium will be used for analyses.

Corrected calcium can be only derived at a certain time points in case both laboratory values total calcium and albumin have been reported for the patient in the same laboratory sample.

Hepatic enzyme elevations (potential Hy's law cases):

These are defined as those cases where a combination of all of the following events occurred: any on-treatment value of ALT and/or AST $> 3\text{ULN}$ (upper limit of normal) with total bilirubin $\geq 2\text{ULN}$. The events can occur in any order, but must occur within 14 days of the previous event, i.e. the second event must occur within 14 days of the first event, and the third event must occur within 14 days of the second event, etc. Patients with missing laboratory values for liver enzymes will be excluded from these analyses, but presented separately.

Tabulations of hepatic enzyme elevations and liver laboratory values will be done according to the FDA Drug Induced Liver Injury (DILI) guidance ([10](#)).

Hepatic enzyme elevations will be displayed for the treated set for the whole on-treatment period.

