Description of change	Vital signs will be evaluated at the time points specified in the flowchart, prior to blood sampling, or after a sufficient period of rest (usually 5 minutes is sufficient, but a longer rest may be required if there are any problems at the blood sampling) .	
Rationale for change	Conditions to assess vital signs were clarified.	
Section to be changed	5.2.3.2 Biochemistry	
Description of change	The standard biochemistry panel will consist of glucose (serum or plasma), sodium, potassium, chloride, calcium, phosphate, urea , serum creatinine (measured by enzymatic assay, Isotope dilution mass spectroscopy [IDMS] standardised Jaffe assay, or non-IDMS Jaffe assay), AST, ALT, alkaline phosphatase, lactate dehydrogenase, gamma glutamyl transferase , bilirubin (total, direct, and indirect bilirubin), haptoglobin, total protein, albumin, urea or urea nitrogen, uric acid and creatine kinase (CK). If CK is elevated, then CK-MB [cardiac], Troponin (either I or T), and myoglobin should be reactively tested.	
Rationale for change	Gamma glutamyl transferase was added to investigate the mechanism of bilirubin elevation. It is clarified that urea and urea nitrogen are interchangeable and testing either one of them based on the availability at the local lab is sufficient.	
Section to be changed	5.2.6.2.3 Pregnancy	
Description of change	
The following paragraph was added:
 
Similarly, potential drug exposure during pregnancy must be reported if a partner of a male trial participant becomes pregnant. This requires a written consent of the pregnant partner. Reporting and consenting must be in line with local regulations. The ISF will contain the trial specific information and consent for the pregnant partner.
	
Rationale for change	To update information on pregnant partner with current template.	
Section to be changed	5.3.1 Assessment of pharmacokinetics	
Description of change	Date and clock times of PK sampling will be recorded in the CRFs, and the following information should be collected in the eCRF for the last 4 days administrations prior to PK sampling and on the day of PK sampling for BI 891065:	

	
1. Date and clock times of drug administration2. Information with respect to food intake (date and time) in case the patient takes the drug after breakfast meals3. If vomiting or diarrhoea occurs within 3 hours after drug administration, the time of the onset of the episode(s)

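### SAP 7.8.2 limits the secondary laboratory tests, including GGT, to a count of flagged patients; this conflicts with Protocol 7.3.5 and with the SAP's own general rule, and is not declared as a change

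*SAP*

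**What the plan says.** SAP 7.8.2 begins with a general rule for laboratory data: "Descriptive statistics, including change from baseline and frequency of patients with transitions relative to the reference range, will be provided". It then sorts the tests into groups.

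- **Primary tests (Table 7.8.2: 1)** get descriptive statistics with change from baseline, shift tables and a frequency table of abnormal patients. ALP, ALT, AST, total bilirubin and creatinine also get shift tables in multiples of the upper reference limit.
- **Secondary tests (Table 7.8.2: 2)** are albumin, aPTT, calcium, chloride, eosinophils, GGT, phosphate, protein, PT and uric acid. For these, "analyses will be limited to frequency of patients with potential clinically significant abnormalities". The GGT row reads "Gamma Glutamyl transferase | High | CTCAE Grade 2 or higher".
- **Later in the section**, a worst value and highest CTCAE grade are calculated for every parameter. Tests without CTCAE grading also get reference-range tables at baseline, maximum and last value.

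Protocol 7.3.5 states: "Laboratory data will be analysed both quantitatively as well as qualitatively". It adds "Treatment groups will be compared descriptively with regard to distribution parameters", alongside the frequencies of abnormal values. No test is excepted.

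SAP section 4, on changes to the planned analysis, states: "All analyses described in the CTP will be carried out".

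GGT is in the current biochemistry panel (Protocol 5.2.3.2). The rationale in Amendment 3 (Protocol 11.3) is: "Gamma glutamyl transferase was added to investigate the mechanism of bilirubin elevation".

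**The concern.** The specific rule for secondary tests takes away what the protocol, and the SAP's own opening rule, promise for all laboratory data. A programmer facing a general sentence and a specific one will follow the specific one. No change-from-baseline table would then be produced for ten continuous measures, and the report would carry an undeclared departure from the protocol.

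For most of the ten tests this is a modest loss. For GGT it is more awkward, because GGT was added for a stated purpose. Bilirubin rose in 7 of 25 monotherapy patients (28%) in the first-in-human trial. The rise appeared dose-dependent, reached Grade 2 at most and had no settled cause (Protocol 1.2.3 and 4.1.2.1). It is also part of the reason given for exploring twice-daily dosing. The useful question about GGT is whether it moves within patients, and whether it does so in those whose bilirubin moves. A count at a grade threshold gives little sight of a moderate rise. A short count could be read in the report as absence of an effect.

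**Working it through.** **1. The text side by side**

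| Place | What it provides for a secondary test |
|---|---|
| Protocol 7.3.5 | Quantitative and qualitative analysis; distribution parameters and frequencies |
| SAP 7.8.2, general sentence | Descriptive statistics and change from baseline |
| SAP 7.8.2, rule for Table 7.8.2: 2 | Frequency of flagged patients only |
| SAP section 4 | No departure from the protocol |

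The third row cannot hold together with the other three. No assumption is needed for this step.

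**2. What GGT receives if the SAP is followed as written**

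GGT gets the count at Grade 2 or higher and the worst value and grade. The reference-range tables do not reach it, because they are for tests without CTCAE grading and the GGT rule uses a grade. A listing is stated explicitly only for tests outside both tables; for GGT it is implied at most. Nothing in the readable text gives its change from baseline except the general sentence that the specific rule overrides.

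**3. How much a count can show at these sizes**

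There is no planned figure to reproduce: Protocol 7.2 plans no test and 7.6 reports no power calculation. Cohorts have at least 3 patients (Protocol 3.1), and the stopping rule asks for at least 6 at the MTD among at least 12 treated (7.1.1). Part A expects about 12 (7.6). The share *p* of patients beyond the cut is not given, so it is an assumption shown as a range.

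Information kept by a yes/no cut, relative to the continuous value, for a shift in a normal mean: φ(c)² / [p(1 − p)], where c is the normal quantile with upper tail p.

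| p beyond cut | 0.50 | 0.20 | 0.10 | 0.05 | 0.02 | 0.01 |
|---|---|---|---|---|---|---|
| Kept | 64% | 49% | 34% | 22% | 12% | 7% |
| Lost | 36% | 51% | 66% | 78% | 88% | 93% |

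Probability that nobody in a cohort of n is flagged: (1 − p)ⁿ.

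| p | n = 3 | n = 6 |
|---|---|---|
| 0.05 | 0.86 | 0.74 |
| 0.10 | 0.73 | 0.53 |
| 0.20 | 0.51 | 0.26 |

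The exact two-sided 95% upper limit after no flags is 1 − 0.025^(1/n). It is 71% for 0 of 3 and 46% for 0 of 6. A zero count therefore excludes very little.

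**The case against.** The case for the SAP has substance, and several stronger readings fail against it.

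- **The tests get more than a bare yes/no count.** Worst value and grade are calculated for every parameter. The ungraded tests (chloride, eosinophils, phosphate, protein, PT) get reference-range tables, and uric acid appears to fall under the rule that gives it the same. This stands. It narrows the gap for those tests, but a worst value is not a change from baseline.
- **The cut has a source.** A reader might think the GGT threshold unsupported, but SAP 7.8.2 names CTCAE v5.0 and the protocol cites it.
- **The bilirubin question has other routes.** Total bilirubin, ALP, ALT and AST keep shift tables, and coproporphyrin is sampled (genotyping was cancelled). GGT's purpose appears only in an amendment rationale, not as an objective. Parts of the SAP are redacted, Table 7.8.2: 1 is unreadable here, and the company laboratory standard is not available. So the inference that the trial cannot answer the question is not supported.
- **Ranking tests by priority is ordinary SAP detail.** That is true, but a ranking that removes an analysis the protocol plans should be declared.

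Two further inferences should be resisted. First, one could simulate a power contrast between mean log change and the count. That needs a GGT baseline level, spread and cut value that the documents do not give, and a paired test that is not planned. An exact paired test also needs six one-way changes to reach p < 0.05 (five give 2 × 0.5⁵ = 0.0625; six give 0.031), so its power is near zero by construction. Such a simulation also contains no bilirubin. Second, the other rows of Table 7.8.2: 2 require worsening, for example "CTCAE grade 2 or greater with an increase of at least one CTCAE grade from baseline", and the GGT row prints no such condition. Whether the grade itself refers to baseline is set by CTCAE, which the documents do not reproduce, so it cannot be concluded that patients abnormal before dosing would be counted.

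**Conclusion.** The point holds as an undeclared conflict between SAP 7.8.2 and Protocol 7.3.5, and as an inconsistency within SAP 7.8.2. Its practical weight falls on GGT, which as written would have no summary of change from baseline.

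The loss of information cannot be fixed at one value. It runs from about 36% to 93% as the share beyond the cut goes from 50% to 1%, under a normal-shift model. A loss of nearly all the information would need about 2% or fewer of patients beyond the cut, which the documents do not show. No power figure should be quoted.

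Only descriptive safety reporting is affected. The MTD, DLT and PK analyses do not depend on it. The conclusion about GGT assumes that no redacted section or company standard supplies the missing display.

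**What to change.** In SAP 7.8.2, replace the limiting sentence so that, for the tests in Table 7.8.2: 2, absolute values and change from baseline are summarised by treatment and visit, with the frequency table kept as an addition. SAP section 7 already prefers medians and quartiles where some values are extreme, which may suit GGT.

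At minimum:

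- move GGT to the primary tests;
- include it in the customised shift tables in multiples of the upper reference limit;
- show it by patient next to total and direct bilirubin and ALP. Marginal summaries alone would not show whether GGT and bilirubin move together; a by-patient display can.

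A summary comparison of patients with and without an on-treatment bilirubin rise is not worth adding. If the three patients already counted at 100 mg before Amendment 3 lack GGT (an assumption), about 12 − 3 = 9 remain. At the first-in-human rate, 0.28 × 9 ≈ 2.5, so one group would hold 2 to 3 patients.

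If the sponsor keeps the restriction, SAP section 4 should declare it with a reason.

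The cost is SAP wording and a few more pages of standard output from data already collected. Sample size, the dose-escalation model and trial conduct do not change.
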